### **5.10 Clinical Criteria for Early Trial Termination**

Early trial termination will be the result of the criteria specified below:

1. Quality or quantity of data recording is inaccurate or incomplete
2. Poor adherence to protocol and regulatory requirements
3. Incidence or severity of adverse drug reaction in this or other studies indicates a potential health hazard to subjects
4. Plans to modify or discontinue the development of the study drug

In the event of Merck decision to no longer supply study drug, ample notification will be provided so that appropriate adjustments to subject treatment can be made.

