### **7.3.3 Immediate Reporting of Adverse Events to Merck and to Prometheus**

#### **7.3.3.1 Merck Serious Adverse Events**

A serious adverse event is any adverse event occurring at any dose or during any use of Merck's product that:

- Results in death;
- Is life threatening;
- Results in persistent or significant disability/incapacity;
- Results in or prolongs an existing inpatient hospitalization;
- Is a congenital anomaly/birth defect;
- Is a new cancer (that is not a condition of the study);
- Is associated with an overdose;
- Is an other important medical event

Refer to Table 6 for additional details regarding each of the above criteria.

Any serious adverse event, or follow up to a serious adverse event, including death due to any cause other than progression of the cancer under study that occurs to any subject from

the time the consent is signed through 90 days following cessation of treatment, or the initiation of new anti-cancer therapy, whichever is earlier, whether or not related to Merck product, must be reported within 24 hours to the Sponsor and within 2 working days to Merck Global Safety.

Non-serious Events of Clinical Interest will be forwarded to Merck Global Safety and will be handled in the same manner as SAEs.

Additionally, any serious adverse event, considered by an investigator who is a qualified physician to be related to Merck product that is brought to the attention of the investigator at any time outside of the time period specified in the previous paragraph also must be reported immediately to the Sponsor and to Merck.

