Listings and summary tables will be provided.

Separate data listings and summaries will be presented for all serious adverse events (SAEs) and deaths.

1. Safety monitoring: Sequential boundaries will be used to monitor dose-limiting toxicity rate. The method is developed by Ivanova, Qaqish, and Schell (Biometrics, 2005) Briefly, the accrual of new patients to the trial will be suspended to accommodate re-evaluation of safety issues if the number of patients with dose-limiting toxicities is equal to or exceeds  $b_n$  out of  $n$  patients who are part of the *combination treatment population* (see table). This is a Pocock-type stopping boundary that yields the probability of crossing the boundary at most 0.05 when the rate of dose-limiting toxicity is equal to the acceptable rate 0.15.

Patients who have already enrolled, but not yet started on treatment with any pembrolizumab, at a point in time at which the accrual was suspended may be treated at the discretion of the investigator based on the safety evaluation.

*FIGURE 9: Table of Pocock boundary evaluation*

| Table for number of patients $k$ and Pocock boundary $b_k$ |   |   |   |   |   |   |   |   |   |    |    |    |    |    |    |    |    |    |    |    |    |    |    |    |  |  |
|------------------------------------------------------------|---|---|---|---|---|---|---|---|---|----|----|----|----|----|----|----|----|----|----|----|----|----|----|----|--|--|
| Number of Patients, $k$                                    | 1 | 2 | 3 | 4 | 5 | 6 | 7 | 8 | 9 | 10 | 11 | 12 | 13 | 14 | 15 | 16 | 17 | 18 | 19 | 20 | 21 | 22 | 23 | 24 |  |  |
| Boundary, $b_n$                                            | - | - | 3 | 3 | 4 | 4 | 4 | 5 | 5 | 5  | 5  | 6  | 6  | 6  | 6  | 7  | 7  | 7  | 7  | 8  | 8  | 8  | 8  | 8  |  |  |
|                                                            |   |   |   |   |   |   |   |   |   |    |    |    |    |    |    |    |    |    |    |    |    |    |    |    |  |  |

If the number of patients  $k$  who have DLT events that are *possibly, probably or definitely* related equals or exceeds the boundary  $b_k$ , the accrual to the trial will be suspended pending reevaluating toxicity by study PI and the Protocol Monitor Committee (PMC). This may include recommendations on patients who have already started on treatment.

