The DLT events for this safety purpose will *exclude* events that are judged by the PI to be typical for IL-2 treatment, referencing the experience as described in the package insert for Proleukin™ and have resolved by the point in time that the next dose of pembrolizumab is due. The DLT events to be counted here will include at least those defined as in section 7.3.4 as these:

- AEs leading to permanent dosing discontinuation of either pembrolizumab or HD IL-2
- AEs  $\geq$  Severity Grade 3 occurring after the HD IL-2 administration dates
- Unexpected (according to medical judgment) AEs
- Additionally, other events that the PI may designate.

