## **10.6 Quality Management System and the PMC**

The principal investigator has the authority to stop the study, including stopping accrual, or stopping protocol-treatment.

The principal Investigator is ultimately responsible for the study.

The principal Investigator will review the Serious Adverse Events

The principal investigator has the authority to stop the study, including stopping accrual, or stopping protocol-treatment.

The adverse event data will be reviewed by the principal investigator in conjunction with the study biostatisticians.

This is an investigator initiated trial, that will be monitored according to the Moffitt Cancer Center Policy for Monitoring of Investigator Initiated Clinical Research. Data will be captured in the Oncore computer database program.

Regulatory documents and case report forms will be monitored internally, according to Moffitt Cancer Center Monitoring Policies.

Monitoring will be performed regularly to verify data are accurate, complete and verifiable from source documents.

Monitoring will be performed to ensure that the conduct of the trial is in compliance with currently approved protocol, and with Good Clinical Practice *guidelines*, and with applicable regulatory requirements.

The study will be reviewed by the PMC for data and safety monitoring. *This is the standard Moffitt Cancer Center Data Safety Monitoring Plan for investigator initiated studies.* The PMC monitors for adverse event reporting, for data and safety monitoring, and internal audit findings. The PMC, upon review of an agenda item, may approve the study for continuation, recommend revisions, or suspend or close a protocol.

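### The only count-based rule that orders an accrual pause (Figure 9) is not reached by one or two related deaths alone, nor by any related death in a patient who never received IL-2

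*Combined protocol and SAP*

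**What the plan says.** **The pause rule.** Section 8.5 uses a Pocock-type sequential boundary (Figure 9). It counts DLTs among "patients who are part of the *combination treatment population", which Figure 7 in section 8.3 defines as at least one dose of pembrolizumab and at least one of IL-2. If the count reaches the boundary, accrual is suspended while the PI and the Protocol Monitor Committee (PMC) re-evaluate toxicity. Patients already enrolled but not yet started "may be treated at the discretion of the investigator based on the safety evaluation".

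**What counts as a DLT.** The list in 8.5 includes adverse events of at least "Severity Grade 3 occurring after the HD IL-2 administration dates", events that end dosing permanently, unexpected events, and "other events that the PI may designate". Grade 5 has no separate rule. The list refers to section 7.3.4, where the Table 6a window opens after the first IL-2 dose.

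**Other safeguards.**
- Section 7.3.3.1: serious adverse events, including deaths not due to progression, "whether or not related to Merck product, must be reported within 24 hours to the Sponsor".
- Section 10.6: the PI will review SAEs and may stop the study. The PMC will review the study and "may approve the study for continuation, recommend revisions, or suspend or close a protocol". The section names the institution's standard "Data Safety Monitoring Plan for investigator initiated studies", which is not among the documents.
- Section 5.10, item 3: early termination follows if "Incidence or severity of adverse drug reaction in this or other studies indicates a potential health hazard to subjects".

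**The concern.** Section 4.4.4.1 explains the formal safety format by noting that these two drugs have not been given together on this schedule before. In that setting one would expect the protocol to say what happens to accrual after a treatment-related death. It gives a firm answer for an excess of DLTs in general, but none for a death as such.

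Pembrolizumab-only exposure is part of the design. Every patient has about 9 weeks of pembrolizumab before the first IL-2 day (section 5.2.2, inclusion criterion 10). The Subject Replacement Strategy also lets some patients continue on pembrolizumab alone for up to 12 doses. Table 2 lists pembrolizumab as the experimental drug, and section 5.2.1.2 warns that its adverse events can appear soon after the first dose. A related death in this group adds nothing to Figure 9.

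What is at stake is whether new patients keep entering while such a death is reviewed. At present that is decided case by case.

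**Working it through.** **1. Reproduce the plan's own figure.** Figure 9 has no boundary at k = 1 or 2. It is then 3 (k = 3–4), 4 (5–7), 5 (8–11), 6 (12–15), 7 (16–19) and 8 (20–24). Let f(k, s) be the probability of s DLTs after k patients without having crossed. With DLT rate p,

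f(k, s) = f(k−1, s)·(1−p) + f(k−1, s−1)·p, keeping only s < b_k.

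The crossing probability is 1 − Σ f(24, s). At p = 0.15 it is 0.0468, which meets the stated limit of 0.05. At p = 0.25, 0.30 and 0.40 it is 0.307, 0.509 and 0.843. The boundary is correctly calculated.

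**2. What a related death does to the count.**

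| Situation | Added to count | Pause required? |
|---|---|---|
| 1 or 2 related deaths in IL-2-treated patients, no other DLT | 1 or 2 | No: below the minimum of 3 at all 22 looks |
| Related death that is itself the DLT reaching the boundary (e.g. third DLT at k = 3 or 4) | 1 | Yes |
| Related death in a patient who never received IL-2 | 0 | No |

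The exclusion in 8.5 for typical IL-2 events needs the event to have resolved by the next pembrolizumab dose, so it cannot remove a death. A related death in an IL-2-treated patient is counted, but only once. The second boundary sentence in 8.5 does not repeat the population limit. Even if it is read as covering everyone treated, one or two deaths alone stay below 3.

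**3. Illustrative size.** The documents give no related-death rate, so q = 1%, 2% or 5% is assumed, as part of a total DLT rate p = 0.15. Then

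P(at least one related death, never crossed) = P(never crossed) − P(never crossed and no death).

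The first term is 1 − 0.0468 = 0.9532. The second uses the same recursion with weights (1−p) for no DLT and (p−q) for a non-fatal DLT.

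| q | Never crossed | Never crossed, no death | Difference |
|---|---|---|---|
| 1% | 0.9532 | 0.7567 | 0.1965 |
| 2% | 0.9532 | 0.5983 | 0.3549 |
| 5% | 0.9532 | 0.2887 | 0.6644 |

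This is for 24 combination-treated patients. The calculation has no calendar in it, so some of these deaths would fall after accrual has closed, when there is nothing to pause.

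**4. Dependence on the DLT rate.** Among trials with a related death, the share in which Figure 9 is never crossed is about 94% at p = 0.15, which largely reflects a boundary built to be crossed at most 5% of the time at that rate. It falls to about 67%, 49% and 18% at p = 0.25, 0.30 and 0.40.

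**The case against.** The strongest reply is that deaths are already well covered. Reporting within 24 hours is compulsory. PI review of SAEs and PMC review are stated as things that will happen. Section 5.10 says termination will result once its criterion is met. A reader might infer that every safeguard for deaths is discretionary; the documents do not support that. Only the decision to pause, or the finding that the 5.10 criterion is met, is a judgment, and 5.10 leads to termination rather than a pause.

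Second, the institutional monitoring plan may contain a rule for related deaths. That stands: silence in this protocol does not show silence in the plan, so the point is confined to this protocol's text.

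Third, limiting Figure 9 to IL-2-treated patients is sensible for monitoring the combination's DLT rate, and both drugs had a record as single agents. That also stands. Figure 9's population, its calibration and its blanks at k = 1 and 2 are not faulted.

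Fourth, the probabilities rest on assumed fatal rates and ignore timing. Section 1.0 estimates enrolment ending 3/2019 and this version is dated 03/16/2020, so the documents do not show whether accrual was still open. This limits the illustration and is why the fix is conditional on open accrual. The structural finding needs none of these numbers.

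**Conclusion.** The point holds in limited form. As this protocol is written, one or two related deaths with no other DLT, or any related death in a patient who never received IL-2, do not oblige anyone to pause accrual. Reporting and review are obligatory; the pause is left to the PI or the PMC.

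This follows from the text of 8.5 and Figure 9 without any modelling. The illustrative chance of a related death with Figure 9 never crossed (0.20, 0.35 or 0.66 in 24 combination-treated patients) rests on assumed fatal rates of 1%, 2% or 5% within a 15% DLT rate and takes no account of when deaths occur.

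It would go too far to conclude that deaths are ignored, that Figure 9 is wrong, or that the institution has no rule of its own. This is an inexpensive patient-safety improvement, not a failure of a stated operating characteristic.

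**What to change.** Keep Figure 9 as it is and add one sentence to section 8.5:

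*Any Grade 5 event at least possibly related to pembrolizumab or IL-2, in the ever-treated population from the first pembrolizumab dose, is referred at once to the PMC, and, if accrual is open, accrual is suspended pending its review with the study PI.*

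This reuses the PI and PMC process already attached to Figure 9 and the ever-treated population already defined for safety in section 8.3. Patients enrolled but not yet started remain under the existing discretion in 8.5. No new committee, data or patients are needed, and the 0.05 limit for Figure 9 is unaffected.

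The cost is a possible temporary pause. In 26 treated patients its probability is at most 1 − (1−q)^26 = 0.23, 0.41 or 0.74 at assumed related-death rates of 1%, 2% or 5%, and lower once deaths after accrual closes are excluded. Section 8.4 counts the 26 as patients with at least one IL-2 dose, so the number ever treated, and with it this ceiling, could be somewhat higher. If the institutional plan already requires such a pause, a cross-reference to it would suffice.

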## 8.6 Correlative studies on specimens of tumor and of blood specimens:

These are all secondary endpoints,

Responders versus remaining patients will be compared.

The following tissue markers will be considered for correlative testing.

- (1) Quantitation of circulating cells with flow cytometry counts for cells with lymphocyte phenotypes of CD3+, CD4+, T-regulatory, CD8+, NK+, MDSC, or DC, and conventional

differential for granulocytes, platelets or other subtypes. The relevant ratios, such as DC: MDSC ratio; CD4+ : CD4/FoxP3+ ratio; CD8+ : NK cell ratio will be computed.

- (2) On the pretreatment tumor specimen, quantitation of infiltrating leukocytes that are positive for CD3, CD4 or CD8, by immunohistochemistry.
- (3) On the pretreatment tumor specimen, quantitation of PD-L1.
- (4) Quantitation of serum cytokines including but not limited to: CXCL9, CXCL10

[figure not shown]
If the data follow a normal distribution, t test will be used for biomarker level comparison. If the data do not follow normal distribution then a power transformation (e.g. square-root, log) or non-parametric Wilcoxon rank-sum test approach will be adopted. The Bonferroni-Holm approach will be used to account for multiple testing to control type I error at 5%. Some tests may be dropped from the multiple testing group prior to analysis after the overall distribution of the biomarker is examined, but before it is divided by response group. Tests outside the multiple testing group will be studied at alpha = .05 individually, and considered as exploratory analyses.

- (5) CD8+ lymphocyte subset analyses of gene expression; using the NanoString product, Multiplexed Cancer Immune Response Analysis nCounter® PanCancer Immune Profiling Panel for Gene Expression. A similar assay on other leukocyte subsets may be performed.

The 760 genes expressed will be compared for the responders versus the nonresponders, for the baseline specimens.

The 760 genes expressed will be compared for the specimens after the 3 on treatment specimens versus baseline specimens.

These analyses will identify genes for which there is a statistically significant difference of expression level. The description of these genes' expression difference will be the endpoint, to address the hypothesis that differences of CD8+ gene expression are a consequence of the treatment with these medications that have targets on lymphocytes.

[http://nanostring.yipkos.com/service/documents/ASCO2016/White%20Papers/NanoString\\_IO\\_White%20paper\\_Final%20\(005\).pdf](http://nanostring.yipkos.com/service/documents/ASCO2016/White%20Papers/NanoString_IO_White%20paper_Final%20(005).pdf)

[http://nanostring.yipkos.com/service/documents/ASCO2016/White%20Papers/LBL-10117-02\\_WP\\_PanCancer\\_Immune\\_Profiling.pdf](http://nanostring.yipkos.com/service/documents/ASCO2016/White%20Papers/LBL-10117-02_WP_PanCancer_Immune_Profiling.pdf)

## **9.1 LABELING, PACKAGING, STORAGE AND RETURN OF CLINICAL SUPPLIES**

### **9.2 Investigational Product**

The investigator shall take responsibility for and shall take all steps to maintain appropriate records and ensure appropriate supply, storage, handling, distribution and usage of investigational product in accordance with the protocol and any applicable laws and regulations.

Clinical Supplies will be provided by Merck as summarized in Table 7.

Table 7 Product Descriptions

| Product Name & Potency | Dosage Form               |
|-----------------------------------|----------------------------------|
| Pembrolizumab 50 mg               | Lyophilized Powder for Injection |
| Pembrolizumab 100 mg/ 4mL         | Solution for Injection           |

### **9.3 Packaging and Labeling Information**

Clinical supplies will be affixed with a clinical label in accordance with regulatory requirements.

### **9.4 Clinical Supplies Disclosure**

This trial is open-label; therefore, the subject, the trial site personnel, the Sponsor and/or designee are not blinded to treatment. Drug identity (name, strength) is included in the label text; random code/disclosure envelopes or lists are not provided.

### **9.5 Storage and Handling Requirements**

Clinical supplies must be stored in a secure, limited-access location under the storage conditions specified on the label.

Receipt and dispensing of trial medication must be recorded by an authorized person at the trial site.

Clinical supplies may not be used for any purpose other than that stated in the protocol.

## **9.6 Returns and Reconciliation**

The investigator is responsible for keeping accurate records of the clinical supplies received from Merck or designee, the amount dispensed to and returned by the subjects and the amount remaining at the conclusion of the trial.

Upon completion or termination of the study, all unused and/or partially used investigational product will be destroyed at the site per institutional policy. It is the Investigator's responsibility to arrange for disposal of all empty containers, provided that procedures for proper disposal have been established according to applicable federal, state, local and institutional guidelines and procedures, and provided that appropriate records of disposal are kept

.

## **10.1 ADMINISTRATIVE AND REGULATORY DETAILS**

### **10.2 Confidentiality**

The data will be maintained on the ONCORE program at the Moffitt Cancer Center. No personally identifiable data will be published.

Outcome data will be available to Merck and to Prometheus.

### **10.3 Compliance with Financial Disclosure Requirements**

All Financial disclosures, relationship to sponsors, will be organized as required by law.

### **10.4 Compliance with Law, Audit and Debarment**

All applicable laws will be complied.

No debarred physicians will be study investigators.

### **10.5 Compliance with Trial Registration and Results Posting Requirements**

Under the terms of the Food and Drug Administration Modernization Act (FDAMA) and the Food and Drug Administration Amendments Act (FDAAA), the Sponsor of the trial is solely responsible for determining whether the trial and its results are subject to the requirements for submission to the Clinical Trials Data Bank, <http://www.clinicaltrials.gov>. Information posted will allow subjects to identify potentially appropriate trials for their disease conditions and pursue participation by calling a central contact number for further information on appropriate trial locations and trial site contact information.

## **10.6 Quality Management System and the PMC**

The principal investigator has the authority to stop the study, including stopping accrual, or stopping protocol-treatment.

The principal Investigator is ultimately responsible for the study.

The principal Investigator will review the Serious Adverse Events

The principal investigator has the authority to stop the study, including stopping accrual, or stopping protocol-treatment.

The adverse event data will be reviewed by the principal investigator in conjunction with the study biostatisticians.

This is an investigator initiated trial, that will be monitored according to the Moffitt Cancer Center Policy for Monitoring of Investigator Initiated Clinical Research. Data will be captured in the Oncore computer database program.

Regulatory documents and case report forms will be monitored internally, according to Moffitt Cancer Center Monitoring Policies.

Monitoring will be performed regularly to verify data are accurate, complete and verifiable from source documents.

Monitoring will be performed to ensure that the conduct of the trial is in compliance with currently approved protocol, and with Good Clinical Practice *guidelines*, and with applicable regulatory requirements.

The study will be reviewed by the PMC for data and safety monitoring. *This is the standard Moffitt Cancer Center Data Safety Monitoring Plan for investigator initiated studies.* The PMC monitors for adverse event reporting, for data and safety monitoring, and internal audit findings. The PMC, upon review of an agenda item, may approve the study for continuation, recommend revisions, or suspend or close a protocol.

## **10.7 Data Management**

Data will be tabulated from source documents and placed into custom forms on the ONCORE program at Moffitt Cancer Center.

## 11.1 APPENDICES

### 11.2 ECOG Performance Status

FIGURE 10: ECOG PS table

| Grade | Description                                                                                                                                                                           |
|-------|---------------------------------------------------------------------------------------------------------------------------------------------------------------------------------------|
| 0     | Normal activity. Fully active, able to carry on all pre-disease performance without restriction.                                                                                      |
| 1     | Symptoms, but ambulatory. Restricted in physically strenuous activity, but ambulatory and able to carry out work of a light or sedentary nature (e.g., light housework, office work). |
| 2     | In bed <50% of the time. Ambulatory and capable of all self-care, but unable to carry out any work activities. Up and about more than 50% of waking hours.                            |
| 3     | In bed >50% of the time. Capable of only limited self-care, confined to bed or chair more than 50% of waking hours.                                                                   |
| 4     | 100% bedridden. Completely disabled. Cannot carry on any self-care. Totally confined to bed or chair.                                                                                 |
| 5     | Dead.                                                                                                                                                                                 |

\* As published in Am. J. Clin. Oncol.: *Oken, M.M., Creech, R.H., Tormey, D.C., Horton, J., Davis, T.E., McFadden, E.T., Carbone, P.P.: Toxicity And Response Criteria Of The Eastern Cooperative Oncology Group. Am J Clin Oncol 5:649-655, 1982.* The Eastern Cooperative Oncology Group, Robert Comis M.D., Group Chair.

